
in that country. The maximum duration of the extension phase will be 2.5 years from the date of the first patient enrolled in that country or until marketed product is available in that country, whichever comes first. Once study closeout date is determined, the site staff is contacted to have the patients return for their extension phase EOS visit. While the extension phase is then deemed complete the safety follow-up is anticipated to be continued in registries following study results and discussion with Health Authorities.

Patients who discontinue study treatment

Every attempt to determine follow-up status of patients who discontinue study treatment, for *any* reason prior to the completion of the trial, must be made unless prohibited by local regulations. It is required that these patients are contacted per study schedule (i.e., every 3 months) to ensure all endpoints (safety and efficacy) are collected and reported. It will be at the discretion of the site staff to determine if these patients will be contacted by phone or attend the regularly scheduled visits.

For patients whose treatment is stopped as a result of a Data Monitoring Committee (DMC) recommendation to suspend treatment in one dose group, follow-up for cardiovascular (CV) and safety events will continue. Since these patients will not receive further study medication, less frequent follow-up will be conducted every 6 months. Continued follow-up will likely enhance understanding of the safety of the other dose groups.

Any patient who stops study treatment, withdraws consent (if re-consented) or becomes no longer lost to follow up, is allowed to restart the study treatment at the discretion of the investigator regardless of length of time off study treatment.

Extension phase: for patients whose status is unclear because they fail to appear for study visits without stating an intention to withdraw, the investigator should show "due diligence" by contacting the patient, family or family physician as agreed in the informed consent and by documenting in the source documents steps taken to contact the patient, e.g. dates of telephone calls, registered letters, etc. A patient should not be formally considered lost to follow-up until his/her scheduled end of study visit would have occurred.

End of Study Follow-up for all prediabetic patients

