Pre-screening is a key element to successfully identifying the correct patients to be screened for this clinical study. All patients should have an available hsCRP value prior to the time of screening (Visit 1). The available hsCRP value should be at least 28 days after a cardiovascular event or procedure or major surgical procedure, and must be less than 60 calendar days prior to screening (Note: centrally-performed hsCRP results must be obtained less than 60 calendar days prior to Visit 2 to be used to evaluate Inclusion criterion 5, [Section 4.1](#)). The Pre-screening visit should be used after review of the patient's charts to determine patient's eligibility and to obtain an hsCRP value. Patients with a prescreen hsCRP ≥ 2 mg/L from the central laboratory do not require a second hsCRP at Visit 1, providing the prescreen hsCRP blood sample is drawn less than 60 days prior Visit 2 and the patient is on a stable (at least 4 weeks) long term (cardiovascular) medications.

Converting to T2DM: Any patient who is reported as having an elevated HbA_{1c} and/or FPG as defined in [Section 4](#), will need to have an unscheduled visit within 6 weeks following the first elevated HbA_{1c} and/or FPG result to assess for conversion from pre-diabetes to T2DM.

[figure not shown]
Discontinuation of study treatment: It is highly encouraged that patients who discontinue study treatment still attend regularly scheduled clinic visits. If the patient does not attend the scheduled visit, site staff are required to make a telephone contact with the patient according to the visit schedule (i.e., every 3 months) to assess for any potential study endpoints and record as appropriately in the eCRFs.

For patients whose treatment is stopped as a result of a data monitoring committee recommendation to suspend treatment in one dose group, follow-up for cardiovascular (CV) and safety events will continue. Since these patients will not receive further study medication, less frequent follow-up will be conducted every 6 months.

Withdrawal of consent or Lost to Follow-Up: Sites are required to provide an annual update in the eCRF's for any patient who has a status of Withdrawal of consent. Please see [Section 5.5.8](#) for any patient who fails to appear for on site visits the study staff will be required to complete the Visit Information eCRF.

For any patients who suffer from a stroke during the pivotal phase please see [Section 6.6.5](#) for details

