Sites are required to call the IVRS/IWRS at the prescreening and screening visit and at each visit to register their patient's status and if applicable, receive the medication numbers to

dispense treatment. Dispensing of medication should be the last assessment performed at each visit.

[figure not shown]
[figure not shown]
[figure not shown]

Table 6-1 Assessment schedule of pivotal phase

Visit	Pre-Screen	1	2	2.5	3	4	5	6	7	8	9	10	11	12,16, 20,24 ⁸	13,17, 21, 25 ⁸	14,18, 22,26 ⁸	15,19, 23,27 ⁸	End of Study (EOS)
Month		-1	0	0.5	1.5	3	6	9	12	15	18	21	24	27,39, 51,63...	30,42, 54, 66...	33,45, 57,69...	36,48, 60,72...	event driven
Obtain informed consent		X																
Prescreening Informed Consent	X																	
Height		X																
Inclusion/Exclusion		X																
Labs for entry criteria only:, HIV Screen, HBsAg and HCV antibody [For Japan only] [In Japan, HBc antibody and HBs antibody are additionally included]		X																
Hs-CRP	X ¹⁰	X ⁷	X	X	X	X	X	X	X		X		X		X		X	X
Determination of tuberculosis status ¹		X																
Demography																		
Demography		X																
History of CV Disease		X																
Medical History/Current Conditions		X																
Family History of CV disease			X															
Smoking & Alcohol History			X															
Treatment Assessments																		
Call IVRS/IWRS	X	X	X	X	X	X	X	X	X	X	X	X	X	X	X	X	X	X
Drug Administration			X	X		X	X	X	X	X	X	X	X	X	X	X	X	
Prior & Concomitant Antidiabetic & CVD Medications		X	X	X	X	X	X	X	X	X	X	X	X	X	X	X	X	X
Concomitant Medications ¹¹		X	X	X	X	X	X	X	X	X	X	X	X	X	X	X	X	X

[figure not shown]
[figure not shown]

Visit	Pre-Screen	1	2	2.5	3	4	5	6	7	8	9	10	11	12,16, 20,24 ⁸	13,17, 21, 25 ⁸	14,18, 22,26 ⁸	15,19, 23,27 ⁸	End of Study (EOS)	
Month		-1	0	0.5	1.5	3	6	9	12	15	18	21	24	27,39, 51,63...	30,42, 54, 66...	33,45, 57,69...	36,48, 60,72...	event driven	
Efficacy Assessments																			
Potential endpoint assessment				X	X	X	X	X	X	X	X	X	X	X	X	X	X	X	X
HbA1c & FPG (all patients) ²		X	X	X	X	X	X	X	X		X		X		X		X		X
Safety Assessments																			
Physical Exam			X						X				X					X	X
Vitals (includes BMI, weight, waist circumference)		X	X	X	X	X	X	X	X		X		X		X		X		X
ECG			X						X				X					X	X
Standard Hematology & Chemistry		X	X	X	X	X	X	X	X		X		X		X		X		X
Fasting Lipid Profile ³		X	X	X	X	X	X	X	X		X		X		X		X		X
Immunological (e.g. ANA) Screen			X																X ¹²
AE (prompting for infections)			X	X	X	X	X	X	X	X	X	X	X	X	X	X	X	X	X

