If the SAE is not previously documented in the Investigator's Brochure or Package Insert (new occurrence) and is thought to be related to the Novartis study drug, a Drug Safety and Epidemiology Department associate may urgently require further information from the investigator for Health Authority reporting. Novartis may need to issue an Investigator Notification (IN) to inform all investigators involved in any study with the same drug that this SAE has been reported. Suspected Unexpected Serious Adverse Reactions (SUSARs) will be collected and reported to the competent authorities and relevant ethics committees in accordance with EU Guidance 2011/C 172/01 or as per national regulatory requirements in participating countries.

Reporting of events (including coincidental cardiovascular events) that are both study endpoints and AE's / SAE during pivotal phase

The integrity of the pivotal phase may be compromised if cardiovascular events that are study endpoints are systematically unblinded in order to fulfill European SUSAR reporting requirements for SAE ([European Commission ENTR/CT12 Guideline \(2006\)](#)). Therefore, in the pivotal phase, potential study endpoints are excluded from the definition of AE's and SAE's and are not to be captured as AE and SAE's but only on the relevant study endpoint CRF. During the pivotal phase, these events are therefore NOT to be reported to Novartis within 24 hours on SAE forms and will not be reported to regulatory agencies or investigators other than as a study endpoint in the Clinical Study Report. Reporting to IRB's should follow local guidelines.

The following pre-defined study endpoints are excluded from the definition of AEs and SAE's in the pivotal phase:

- CV and non-CV Deaths (please see section Reporting of Deaths for specific exceptions for selected non-CV deaths that must be reported as both endpoints AND SAEs)
- Fatal and non-fatal MI
- Fatal and non-fatal Stroke (e.g. hemorrhagic stroke, ischemic stroke)
- [REDACTED]
- [REDACTED]
- Hospitalization or prolongation of hospitalization for heart failure
- Critical Limb ischemia

- Limb amputation
- Transient Ischemia Attack (TIA)
- New onset type 2 diabetes (NOD)
- [REDACTED]
- Coronary angiography / Coronary Revascularization (PCI or CABG)
- [REDACTED]
- [REDACTED]

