15.8 Definition of New Onset Diabetes

The clinical definition of Type 2 diabetes consists of the following:

- a. Presence of Fasting Plasma Glucose measured on two consecutive occasions ≥ 126 mg/dl (≥ 7.0 mmol/L) within 6 weeks (the Event Date will be the first of these two occasions)
Or
- b. Presence of HbA1c measured on two consecutive occasions ≥ 6.5 % within 6 weeks in a laboratory which has validated compliance of a test that conforms to the National Glycosylation Standards Program ([Little et al 2010](#)) reference measurement of HbA1c (the Event Date will be the first of these two occasions)
Or
- c. The institution and use of a diabetes medication for the purpose of glucose control by the patient including all oral agents, insulin, and injectable GLP-1 analogs. (the Event Date will be the Date noted on the prescription)
- d. In the event wherein a patient has one laboratory parameter which would place them in the NOD category if repeated and confirmed within 6 weeks, then has a subsequent measurement another parameter which similarly would place them in the NOD category if repeated and confirmed within 6 weeks (e.g. FPG ≥ 126 mg/ dl (≥ 7.0 mmol/L) followed

by HbA1c \geq 6.5%, or vice versa) will be considered to have NOD (the Event Date will be the first of these 2 occasions).

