#### **Time-to-event variables**

Regarding time-to-event variables only observed/reported events will be used in the analysis – i.e. events will not be imputed for censored patients, except for specific sensitivity analyses. This means that in the primary analysis censoring of non-observed events will be assumed to be non-informative. Incomplete dates of events and censoring dates will be imputed as described below.

In the primary analysis, all patients, including those who discontinue study therapy due to lack of efficacy, adverse events or abnormal laboratory values, will be followed until death or the end of the study. Information on patients discontinuing study drug or participation in trial visits will be collected whenever possible and will be used in the analysis.

In general, every effort will be made to collect information about the primary outcome events for those patients who discontinued treatment or their participation in the trial. In patients who could not be followed up for primary outcome events, it is aimed to at least determine the vital status of the patients at the final visit.

The following rules will be applied separately for the composite MACE endpoint and for all its individual components. Patients who have not experienced the respective endpoint will be censored on the date of the last follow-up defined as the earliest of:

- the date of death unless the patient withdrew his consent for the collection of follow-up information,
- the date of the last visit satisfying at least one of the following:
  - yes to the question of “indicates if the subject attended the scheduled visit” on the Visit Information CRF
  - yes/no to the question of “any clinical events since last visit” on the Visit Information CRF

- yes/no to the top three questions (death, myocardial infarction, stroke) on the Clinical Event Tracking CRF.

Should the censoring date lie after the chosen analysis cut-off date, it will be set to the analysis cut-off date. Note that this censoring date should be derived independently of any specific analysis other than all cause mortality, because it will be used to describe the extent of follow-up for (potentially multiple) cardiovascular events and for multiple different time-to-event analyses (e.g. time to MACE, time to MI, analyses of multiple cardiovascular events). For all-cause death, the censoring will occur at the minimum of withdrawal of consent, last known alive date and analysis cut-off date.

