**Figure 6-1 Simplified overview of the adjudication process**

### 6.1.2 Primary efficacy variable

The primary efficacy variable is the time to first occurrence of a major adverse cardiovascular event (MACE) confirmed by Clinical Events Committee (CEC) adjudication, which is a composite endpoint consisting of CEC confirmed cardiovascular death, CEC confirmed MI, and CEC confirmed stroke.

The primary clinical endpoint MACE is a well-established endpoint for CV trials. An external Clinical Events Committee (CEC) will review and adjudicate all clinical events that constitute MACE and the key components of secondary endpoints on a blinded basis as described in section 6.1.1.

The individual components of MACE will be also analyzed as part of the primary efficacy analysis.

- Cardiovascular death
- Myocardial infarction (fatal or non-fatal)
- Stroke (fatal or non-fatal)

[figure not shown]
The time-to-event is computed as the number of days from randomization to the onset of the primary endpoint event. In the case of patients dying due to a MI, the date of the MI and not the date of death is considered to be the date of the endpoint. Data on patients who do not reach the primary endpoint by the study end date will be censored at the latest date they are known to be at risk.

Unless otherwise specified all time-to-event analyses will be based on events occurring during the double-blind phase (i.e. both the double-blind treatment phase and the post-treatment phase). This means that only events between a patient’s randomization and the first of either

1. the patient’s entry into the wash-out period (= end of study visit for the main study),
2. or the patient’s entry into the long-term safety extension study (=end of study visit for the main study),
3. or for those patients proceeding to neither wash-out period nor safety extension the patient’s end of study visit, but only if it occurred during the close-out period,
4. or otherwise the analysis cut-off

will be counted in these analyses as shown in Figure 6-2.

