**Figure 6-5 Closed testing procedure with full details of testing of key secondary endpoints**

This figure as compared to [Figure 6-4](#) shows the full details of the Bonferroni-Holm procedure for the key secondary endpoints in a graphical form, but is otherwise identical in content.

Based on this testing procedure, once the primary null hypothesis for a dose has been rejected the key secondary endpoints for that dose are tested using a weighted Bonferroni-Holm test ([Holm 1979](#)) at the available local significance level for the key secondary endpoints for that dose. The weighting of this Bonferroni-Holm procedure will be 90% for the key secondary CV composite and 10% for the key secondary new onset of diabetes endpoint.

The secondary efficacy variable corresponding to new onset diabetes in patients with pre-diabetes at randomization will be the time from randomization to the first of repeated FPG  $\geq$  126 mg/dL or the first of repeated HbA1c  $\geq$  6.5% or start of new anti-diabetic concomitant medication(s) for glucose lowering purpose. All identified cases of new onset of diabetes will be confirmed by the adjudication committee.

Due to the discrete nature of the visits when new onset of type 2 diabetes can be determined, events identified at the same visit time point as defined in [section 2.3.6](#) for different patients will be considered as tied events and the exact method for handling ties will be used. This assumes that for each of these patients new onset of diabetes occurred at some time point since the previous visit, but that due to the impossibility of continuous monitoring of the patients the true order in which each of them progressed to diabetes is unknown ([Allison 1995](#),

pp. 127 to 137). For this variable patients without new onset of diabetes will be considered censored at the time of their last laboratory assessment. Patients not diagnosed at a regular visit or at the study completion visit will be assigned to one of the scheduled visits as per the algorithm in [section 2.3.6](#).

Subgroup analyses as specified in Table 2-3-1 will be conducted for the key secondary new onset of diabetes endpoint. These will include subgroup analyses by race, which could potentially influence HbA1c levels.

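### New-onset diabetes: drug starts count after the last lab test but event-free patients are censored at it, so event rates run high and the dose comparison is exposed if lab drop-out differs by arm

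*SAP*

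**What the plan says.** **Event side.** SAP 6.3.2 and Protocol 9.5.1 define NOD in patients with pre-diabetes at randomization as a repeated high FPG, a repeated high HbA1c, or the start of a glucose-lowering drug. For the drug route, Protocol 15.8(c) says that "the Event Date will be the Date noted on the prescription" and asks for no lab result. SAP 6.1.2 says that time-to-event analyses "will be based on events occurring during the double-blind phase (i.e. both the double-blind treatment phase and the post-treatment phase"). No passage limits drug starts to the time before the last lab test. Events are then tied by visit time point, and a diagnosis made off schedule is assigned to a scheduled visit (SAP 6.3.2, with the windows in SAP 2.3.6).

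**Non-event side.** SAP 6.3.2 states that "patients without new onset of diabetes will be considered censored at the time of their last laboratory assessment". Protocol 9.5.1 has the same sentence.

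**Follow-up without labs.** For patients who stop treatment, Protocol 3.1 leaves it to site staff to decide "if these patients will be contacted by phone or attend the regularly scheduled visits". If they do not attend, Protocol section 6 requires sites to "make a telephone contact with the patient according to the visit schedule (i.e., every 3 months) to assess for any potential study endpoints", and Protocol 7.2 lists NOD among the endpoints. SAP 2.3.9 adds: "Information on patients discontinuing study drug or participation in trial visits will be collected whenever possible and will be used in the analysis". In Protocol Table 6-1 the row "Prior & Concomitant Antidiabetic & CVD Medications" is marked at every visit from screening on, while HbA1c and FPG become six-monthly after month 12.

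**Planned sensitivity work.** SAP 6.3.2 plans NOD analyses on each diagnostic criterion separately. None changes the censoring rule.

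**The concern.** The two rules use different ends of observation. After the last lab, a patient who later starts a drug stays at risk until that event, while one who does not is removed at the last lab. Membership of the risk set then depends on a future outcome, which neither the log-rank test nor the Cox model allows.

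Two things follow. Event rates are too high in every arm, because off-lab time is dropped only for event-free patients. And if the arms lose lab follow-up at different rates, the inflation differs by arm and moves the hazard ratio. Stopping visits can depend on treatment, for example through adverse events or perceived lack of effect. NOD is in the alpha-controlled family (H13, H23, H33).

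**Working it through.** The documents give no NOD figure to reproduce, so the check sets the rules side by side and then sizes the effect under stated assumptions.

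**1. Example.** Two patients have their last HbA1c/FPG at month 12 and are then followed by phone. One starts a drug at month 48: the event goes to the month 48 window and adds 36 months at risk. The other has no event and leaves at month 12. A start at month 14 (14 × 365.25/12 = day 426) lies in the month 12 window of SAP Table 2-4 (days 321 to 457) and adds no time. Window mapping thus removes the mismatch only when the start and the last lab share a window.

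**2. Inputs.** From the documents: 35% pre-diabetic (Protocol 4), 3333 placebo and 2253 patients at 300 mg (Protocol 5.2), so 0.35 × 3333 ≈ 1,167 and 0.35 × 2253 ≈ 789. Assumed: NOD rate 4 per 100 patient-years, 4 years of follow-up, drug-start share p = 0.5, a share d of each arm stopping labs at a uniformly distributed time, and a share r of those staying in phone follow-up. No true treatment effect.

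**3. First-order formula** (ignores depletion by events and the extra time of post-lab cases). The off-lab share of time is f = d/2. Counted events are proportional to (1 − f) + p·r·f and counted time to (1 − f), so each arm's rate is multiplied by 1 + p·r·f/(1 − f). The null HR is the active factor divided by the placebo factor.

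| Lab drop-out, placebo / active | r | Placebo factor | Active factor | HR, formula | HR, simulated | One-sided error at nominal 2.5% |
|---|---|---|---|---|---|---|
| 20% / 20% | 1 | 1.056 | 1.056 | 1.00 | 1.00 | about 2.5% |
| 25% / 15% | 1 | 1.071 | 1.041 | 0.97 | 0.97 | 3.6 to 4.6% |
| 25% / 15% | 0.5 | 1.036 | 1.020 | 0.985 | 0.987 | 3.2% |
| 30% / 10% | 1 | 1.088 | 1.026 | 0.94 | 0.95 | 5.5 to 6.6% |
| 15% / 25% | 1 | 1.041 | 1.071 | 1.03 | 1.03 | not tabulated |

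With equal drop-out the rate is 4.22 by formula and 4.21 by simulation, instead of 4.00. In the 25%/15% case with full retention, repeat runs gave 3.9 to 4.6% with exact dates and 3.6 to 3.7% with Table 2-4 windows. One run averaged 275 events, 15 of them after the last lab (15/275 = 5.5%). The runs used a two-arm log-rank test without strata; Monte Carlo error on the percentages is about 0.25 points at 4,000 trials.

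**4. A second model**, with the Table 6-1 lab schedule, an EOS test for patients still having labs, and labs stopping at a constant yearly rate. About 90% of post-lab drug starts fell in a later window than the last lab. At p = 0.5, stopping at 6% (placebo) versus 3% (active) per year gave HR 0.97 and error 4.3 to 4.6%. Reversing the rates gave HR about 1.02 and error 1.3%. Equal stopping left HR at 1.00 under the null and about 0.80 when the true HR was 0.80.

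**5. One shared limit at the last lab.** Counted events and time are both proportional to (1 − f), so the factor is 1. Simulation gave HR 0.99 to 1.01, rate 4.00 and error near 2.5%.

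**6. Censoring at last contact instead.** With r = 1 the factor is 1 − (1 − p)·f. At 20% drop-out the rate is 4 × 0.95 = 3.8. At 25%/15% the HR is 0.9625/0.9375 = 1.03, and at 30%/10% it is 0.975/0.925 = 1.05. Simulation agrees (1.03 to 1.05). This rule is biased too, because lab-defined NOD cannot be found once testing stops.

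**The case against.** Several points on the other side stand.

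- The prescription date is not the analysis time. Mapping to visit windows absorbs drug starts shortly after the last lab and lowers the error somewhat. It leaves about 90% of them in a later window.
- The planned FPG-alone and HbA1c-alone analyses contain no post-lab drug starts and are free of the problem. The alpha-controlled analysis and the drug-start-alone analysis are not.
- SAP 7.3.1 already tabulates NOD by drug start versus lab criteria per arm, though not by timing relative to the last lab.
- Full phone retention is generous. With half retained HR is about 0.99, and with a quarter 0.992. A milder imbalance of 22.5% versus 17.5% with full retention gives HR 0.988 and error 2.9%. Injections are given on site, discontinuers are urged to keep attending, and HbA1c/FPG is taken at EOS, all of which limit off-lab time.
- The adjudication charter and the dataset specifications are not in these documents and could set a limit on late drug starts. The protocol and SAP as written do not.

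A reader might infer that the NOD comparison is biased towards canakinumab. The documents do not support that. They give no lab drop-out by arm, none of their text implies an imbalance in this blinded trial, and an imbalance the other way would work against the drug. A reader might also take the percentages above as trial-wide error rates. They are not: NOD is tested only after the dose's primary hypothesis is rejected, and initially at 10% of the alpha passed on.

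**Conclusion.** The mismatch is real and follows from the stated rules. Post-lab time in patients followed without labs enters the risk set only if an event occurs in a later visit window. Event rates are overstated in every arm, by about 5% under the 20% drop-out assumption (4.21/4.00). The hazard ratio and log-rank test are affected only if lab drop-out differs by arm; with balanced drop-out no bias in the comparison is claimed.

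Under a moderate imbalance the HR moves by about 0.01 to 0.03, and the error of a single one-sided 2.5% test rises to between about 3% and 4.6% when placebo loses more labs. These sizes rest on an assumed NOD rate, drug-start share, lab drop-out and phone retention, none of which the documents give. The point merits correction because the remedy is cheap and the imbalance cannot be known before unblinding.

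**What to change.** Before unblinding, add to SAP 6.3.2 an analysis in which events and non-events share one end of observation: count committee-confirmed NOD only up to the patient's last HbA1c/FPG assessment (or the end of its visit window) and censor all others at that same point. Make this the main rule if Protocol 9.5.1 is amended or clarified to match, since it carries the current censoring sentence and Protocol 11.1 requires a written amendment for a change. Otherwise pre-specify it as a sensitivity analysis, which needs only the SAP.

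Report by arm the number of drug-start events after the last lab and the time from last lab to last contact. If an analysis censoring at last contact is also shown, state that it is not unbiased and why.

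The cost is one derivation rule on lab, drug-start and contact dates that are already collected. The downside is that a few confirmed events after the last lab are left out of the shared-limit analysis, although SAP 2.3.9 intends such information to be used; the by-arm report keeps them visible.

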Given some patients may have medical conditions that elevate their HbA1c levels that are unrelated to diabetes (e.g. patients with hemoglobinopathies such as sickle cell disease, while several other conditions causing interference such as e.g. uremia, liver disease, alcoholism and drug (opiate) use are excluded from this protocol), a second set of new onset diabetes criteria will be defined. This second set of criteria will determine new onset diabetes for these patients based on having either (2 consecutive HbA1c  $\geq 6.5$  % and 2 consecutive FPG values  $\geq 126$  mg/dL from the same visits as HbA1c) or (HbA1c  $\geq 6.5$  % at one visit reported and FPG  $\geq 126$  mg/dL reported at same visit and FPG  $\geq 126$  confirmed at the consecutive visit) or 2 consecutive FPG values  $\geq 126$  mg/dL. The identification of these patients will be done in a blinded fashion by a medical monitor using medical history data and other baseline data. All patients deemed not to have any of these medical conditions will be assessed for new onset diabetes as described in the first set of criteria (see paragraph above). New onset of diabetes data will be reported overall and separately for these patients in whom diagnoses based on HbA1c levels is not appropriate (defined as “FPG  $\geq 126$  mg/dl at 2 occasions” or “Confirmed prescription and use of Diabetes Drug” based on the New Onset Diabetes (Adjudication) CRF page) The analysis described above will also be performed using this alternative new onset diabetes definition.

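### SAP 6.3.2 gives two conflicting definitions of new onset diabetes for patients with unreliable HbA1c: one omits start of a glucose-lowering drug, the other includes it

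*SAP*

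**What the plan says.** The main definition of new onset diabetes in SAP 6.3.2 has three routes: repeated FPG of 126 mg/dL or more, repeated HbA1c of 6.5% or more, and drug start, with committee confirmation of every case: "or start of new anti-diabetic concomitant medication(s) for glucose lowering purpose. All identified cases of new onset of diabetes will be confirmed by the adjudication". Protocol 9.5.1 has the same three routes. Protocol 15.8 makes drug start an event in its own right under item (c): "The institution and use of a diabetes medication for the purpose of glucose control by the patient".

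SAP 6.3.2 then turns to patients whose HbA1c is raised for reasons unrelated to diabetes, such as hemoglobinopathies. A medical monitor identifies them blind from medical history and other baseline data. For them, "This second set of criteria will determine new onset diabetes for these patients based on having either" one of three alternatives, and the list ends with "FPG $\geq 126$ confirmed at the consecutive visit) or 2 consecutive FPG values $\geq 126$ mg/dL". Everyone else stays on the main definition, which the SAP calls the first set.

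Further on, the paragraph says that results will be reported overall and separately for patients in whom HbA1c-based diagnosis is not appropriate. A parenthesis there, taken from the adjudication CRF page, gives the rule as FPG of 126 mg/dL or more on two occasions, or "Confirmed prescription and use of Diabetes Drug". The paragraph closes: "The analysis described above will also be performed using this alternative new onset diabetes definition".

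**The concern.** One paragraph holds two rules for the same patients, and they differ on whether starting a diabetes drug is an event. The stated reason for a second set is interference with HbA1c. That explains dropping HbA1c as a sole criterion. It does not explain dropping the drug route, which the SAP's main definition and Protocol 9.5.1 and 15.8(c) all keep.

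The case at stake is a flagged patient who is put on a drug after one high FPG, or on clinical grounds, and whose glucose then falls. Under the list this patient may never qualify. SAP 6.3.2 censors patients without new onset diabetes at their last laboratory assessment, so the patient would stay in the risk set as free of diabetes until then. Under the parenthesis the same patient is an event. A programmer could follow either text, and a difference from the main result could then arise from the drug route and have nothing to do with HbA1c interference.

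**Working it through.** The plan gives no figure to reproduce, because this is a question of definition. The two rules can be compared by logic.

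**Inputs (SAP 6.3.2).** Take two consecutive visits. Let h1 and h2 mean HbA1c of 6.5% or more at each visit, f1 and f2 mean FPG of 126 mg/dL or more at each visit, and d mean that a new antidiabetic drug was started.

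**The list.**
- Route 1: h1 and h2 and f1 and f2.
- Route 2: h1 and f1 and f2.
- Route 3: f1 and f2.

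Routes 1 and 2 each contain f1 and f2, so any patient meeting either also meets route 3. The union of the three is route 3 alone, and the HbA1c clauses change no patient's classification.

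**The parenthesis.** (f1 and f2) or d.

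**Comparison.** Five yes/no items give 2^5 = 32 patterns.
- Without drug start: 16 patterns. The two rules agree in all of them.
- With drug start: 16 patterns. The parenthesis counts all 16 as events. The list counts only those with f1 and f2 both present: 1 FPG combination × 4 HbA1c combinations = 4. The other 16 − 4 = 12 are non-events under the list.

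The rules therefore disagree in 12 of 32 patterns, and every disagreement involves drug start. Enumerating the patterns by computer gave the same counts. They are logical patterns, not patient frequencies.

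**Limit of the check.** With only two visits, two consecutive values and two occasions are the same thing. Over longer follow-up they need not be, since the parenthesis does not require the two values to be consecutive. Protocol 15.8(a) requires two consecutive occasions within 6 weeks. This is a second, smaller difference to settle in the same edit.

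**Which rule governs?** The closing sentence speaks of an alternative definition right after the parenthesis, which points to the rule that includes the drug. The sentence that introduces the list says that the list decides the endpoint for these patients, which points the other way. The text does not resolve this.

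**The case against.** The strongest reply is that this is only an unclear cross-reference. By nearest antecedent, the alternative definition is the parenthesis, which counts drug start, and then no case is lost. That reading is fair, but the list would then be wrong as written and would still need correcting.

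Three stronger readings are tempting, and the documents do not support them.
- **That every diagnosed and treated flagged patient is lost.** A patient with two consecutive FPG values of 126 mg/dL or more who is then treated is an event under either rule.
- **That the alternative analysis drops all drug-start cases across the prediabetic population.** The second set is for the flagged patients, and unflagged patients are assigned to the main definition. The documents give neither the number flagged nor the share of diagnoses made by drug start, so no percentage loss can be stated.
- **That the key secondary tests (H13, H23, H33) are altered.** They use committee-confirmed diabetes, the protocol's endpoint definitions include 15.8(c), and the alternative analysis is worded as an additional one. The sentence assigning only unflagged patients to the main definition leaves some doubt, but no effect on these tests is shown.

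It can also be said that drug-start cases remain visible elsewhere. The supportive analyses in SAP 6.3.2 run each criterion alone, and SAP 7.3.1 tabulates diabetes by drug start and by laboratory criteria. That would help to trace a discrepancy. It does not say which rule to program.

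Finally, a drug may be started because of a falsely high HbA1c, so counting drug start can let back in some of the interference that the second set is meant to remove. This is a real but small trade-off. The SAP does not give it as a reason for the omission, and its own parenthesis already accepts confirmed drug use in these patients.

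**Conclusion.** The contradiction is real and can be read directly from SAP 6.3.2. The three-route list reduces to two consecutive FPG values of 126 mg/dL or more and has no drug route. The parenthesis in the same paragraph has one, as do the main SAP definition and Protocol 15.8(c).

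The consequence is conditional. A case is lost only if the list is the operative rule, and only for a flagged patient who starts a glucose-lowering drug without two consecutive high FPG values. How many such patients there would be cannot be worked out from the documents, and the number may be small: SAP 6.3.2 notes that several conditions that interfere with HbA1c are already excluded by the protocol. This is a low-severity point, worth correcting because the rule contradicts itself and the correction is cheap.

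**What to change.** In SAP 6.3.2, replace the list with one second set: repeated FPG of 126 mg/dL or more, or confirmed start of antidiabetic medication for glucose lowering. This agrees with the adjudication CRF wording in the parenthesis and with Protocol 15.8(c). Say whether repeated means two consecutive occasions within the 6 weeks of Protocol 15.8(a). Drop the two HbA1c routes; this is editorial, since they add no cases.

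Then state three things: that the alternative definition in the closing sentence means this set; in which patients it applies; and whether it enters the key secondary test or only the additional analysis. Make the change before unblinding.

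The cost is a few words. The CRF wording quoted in the SAP already names both items, so no new data are needed. The one small downside is that a drug started solely because of a falsely high HbA1c would count as an event. The single-criterion sensitivity analyses already planned in SAP 6.3.2 can show how far drug start drives the result.
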